8 STUDY ASSESSMENTS AND PROCEDURES

The following study assessments and procedures will be performed according to the schedule provided in section [1.3](#).

8.1 SCREENING PROCEDURES

8.1.1 Screening Activities Performed Prior to Obtaining Informed Consent

Potential study participants may be identified by medical chart review, from referrals, or from a response to a study advertisement, and initially contacted by a member of the study team in person, by videoconference, over the phone, or by email. During this initial contact, the potential participant will be provided information on the study and asked to provide verbal permission for screening. If a participant provides verbal permission for screening, they may be screened remotely via an NIH-approved videoconferencing platform/by phone/by email. Medical records, including imaging and laboratory studies, may be requested and reviewed by the study team, demographic information will be collected, and concomitant medications will be reviewed.

Participants will be asked about their reaction to the first dose of the COVID-19 vaccine as well as control of their other allergic diseases (e.g., asthma, atopic dermatitis) and other comorbidities

(if present) that may increase their risk of having a severe allergic reaction. Screened individuals who are found to be eligible or potentially eligible for enrollment and are interested in participating in the study will be scheduled for a Visit 1 at the study site. Individuals may be consented to the protocol up to Day -60 by phone/videoconference or in-person at Visit 1. In some cases, individuals with comorbidities that may increase study risks may be asked to come to the NIH Clinical Center for additional screening (see section 8.1.2).

8.1.2 Screening Activities Performed After a Consent for Screening Has Been Signed

Individuals with comorbidities identified at initial screening that may place them at higher risk for having a severe allergic reaction will be asked to come to the NIH for additional screening procedures (e.g., pulmonary function testing, chest X-ray, ECG, echocardiogram, flexible nasolaryngoscopy, and blood laboratory testing) to ensure the individual is stable to undergo the study intervention. Written informed consent to participate in this study will be obtained (either by phone or in person) before any of these additional screening procedures are performed. Individuals who are found not to be eligible to undergo the study intervention after these screening tests will be considered screen failures.

Screening procedures must be completed within 30 days prior to Day 1. Eligibility will be confirmed at Day 0 after pregnancy test (if applicable) and SARS-CoV-2 test results are known.

8.2 EFFICACY ASSESSMENTS

8.2.1 Clinical Evaluations

Demographics: Basic demographic information will be collected.

Medical and medication history/concomitant medication review: At screening (see above), we will review NIH and off-site medical records, as applicable, and interview participants to collect information about conditions or medications that may impact study eligibility or risk of developing severe allergic reactions to the study vaccinations. After enrollment, reviews will focus on updates since the last assessment, with a particular focus on new symptoms and AEs.

Targeted physical exam: Targeted physical exams will be conducted by a study physician or other qualified medical professional prior to each study vaccination and at other timepoint(s) as needed to assess new symptoms or AEs. A targeted physical exam may be conducted at screening for individuals asked to come to the NIH for additional screening procedures to assess the status of comorbid conditions.

Vital signs: Temperature, pulse rate, respiratory rate, oxygen saturation, and blood pressure will be measured within 30 minutes prior to each study vaccination, at the time of blood draws, and as clinically indicated after each study vaccination during Visit 1. At Visit 4, for participants who receive the booster dose, vital signs will be checked at baseline and prior to discharge, and as indicated in case of development of symptoms of an allergic reaction; otherwise, vital signs will be obtained per clinical routine at Visits 3, 4, and 6. Vital signs may be measured at screening for individuals asked to come to the NIH for additional screening procedures to assess the status of comorbid conditions.

Height and weight: Growth parameters (height and weight) will be measured prior to the first study vaccination.

Peak flow measurement and impulse oscilometry: Peak expiratory flow and respiratory resistance of the lungs will be measured by standard methods prior to each study vaccination on days 1 and 2. May be repeated during Visit 1 or at follow-up visits at investigator discretion.

Nasal swab: A nasal swab (mid-turbinate or nasopharyngeal per current Clinical Center practice) will be collected by standard methods prior to the first study vaccination for SARS-CoV-2 testing by PCR. If the SARS-CoV-2 result is positive, Visit 1 will be delayed until the participant has recovered and is outside of the quarantine window.

Pregnancy test: Serum pregnancy testing will be performed for participants of childbearing potential. The result must be confirmed negative prior to proceeding with the study vaccination (at Visit 1) and booster dose (as applicable at Visit 4).

Skin testing: Skin allergy testing to the vaccine, PEG-polysorbate 80-containing medications, and/or other allergens will be conducted according to practice parameters and recent guidelines[32, 33]. In general, all participants will undergo skin prick testing at Visit 3 or Visit 4. If skin prick testing is negative, intradermal allergen testing will be performed. However, the type and nature of the skin testing performed may change in accordance with standard practice, as guidelines are continually updated.

Urine collection: One void prior to each study vaccination and an additional void(s) after each study vaccination and/or the onset of an allergic reaction will be collected using standard methods at Visit 1. At Visit 4 (participants who opt in to booster dose only), one void prior to the booster dose and the first void post-dose will be collected, if possible. Urine samples will be used for laboratory testing (section 8.2.2) and storage.

IV insertion: Two peripheral IV lines will be inserted for Visit 1 by qualified personnel using standard methods to allow for frequent blood draws and rapid administration of fluids/medications if needed in the event of a reaction. For participants receiving a booster vaccination at Visit 4, a single IV line will be inserted prior to booster administration to allow for serial blood draws and rapid administration of fluids/medications if needed in the event of a reaction.

Blood collection: Blood samples will be collected from an IV line when possible, or via venipuncture using standard methods, for laboratory testing (section 8.2.2) and storage. During visit 1, samples will be collected before each study vaccination and approximately 35 minutes (+/-15 minutes), 2 hours (+/-30 minutes), 6 hours (+/-30 minutes), and 24 hours (+/-1 hour) after each study vaccination. The 24-hour blood draw for day 1 will also serve as the baseline blood draw for day 2. An additional blood draw will occur on day 3 of visit 1 prior to discharge. Approximately 464.5 mL of blood will be obtained at visit 1. Approximately 71 mL will be obtained at visit 3, at visit 4, and at visit 6; for participants who opt in to the booster vaccination at Visit 4, the total volume for that visit will be 245 mL. Additionally, up to 150 mL of blood may be collected from participants seen at unscheduled visits (due to AE development or other

study-related concern); however, blood collection would be restricted to only clinically indicated laboratory assessments if the maximum blood volume allowed for research purposes has been reached. Weight-based adjustments to blood volumes collected for research testing will be made as needed for minor participants to remain within the limits allowed at the CC.

Clinical photography: If a participant develops a skin rash after receiving a study vaccination, photographs of the affected area(s) may be taken with the participant's permission. Identifiable photographs will be kept in a secure database and will not be released without the permission of the study participant. Participants will sign the standard NIH photography consent form before photographs are taken.

Anxiety/mental health assessments: The following standardized questionnaires assessing past and current mental health and anxiety will be completed by the participant through the research electronic data capture (REDCap) system (on an electronic device during an in-person visit or by accessing a link sent by email) or on paper:

- Mental health history questionnaire
- Impact of Events Scale-6
- State-Trait Anxiety Inventory
- Generalized Anxiety Disorder-7 scale
- Patient Health Questionnaire-9
- World Health Organization Disability Assessment Schedule-2

Only participants who speak English or Spanish will complete these questionnaires, as these are the only languages in which they are available.

All participants will be asked to rate their current level of anxiety based on a 10-point scale at several different timepoints during the study.

Mental health questionnaire results will be reviewed and relaxation strategies and other recommendations will be provided by a National Institute of Mental Health mental health clinician via a brief telehealth appointment (prior to admission). Subsequent sessions will be scheduled as needed based on ongoing reviews of mental health/anxiety assessments. Participants may be given informational materials to help manage stress.

A brief questionnaire to garner participant feedback on the perceived benefits and burdens of the mental health assessments conducted on this study will be administered at month 5.

Pulmonary function testing: Pulmonary function tests will be performed using standard methods at screening, only for individuals with comorbidities that increase their risk of developing a severe allergic reaction to the study vaccination(s).

Chest X-ray: Chest X-ray will be performed using standard methods at screening, only for individuals with comorbidities that increase their risk of developing a severe allergic reaction to the study vaccination(s).

ECG: ECG will be performed using standard methods at screening, only for individuals with comorbidities that increase their risk of developing a severe allergic reaction to the study vaccination(s).

Echocardiogram: Echocardiogram will be performed using standard methods at screening, only for individuals with comorbidities that increase their risk of developing a severe allergic reaction to the study vaccination(s).

Flexible nasolaryngoscopy: Flexible nasolaryngoscopy will be performed using standard methods to allow assessment of the airway at screening, only if there is concern that a participant may have a difficult airway (e.g., due to history of laryngeal trauma, neck/thyroid surgery, etc).

8.2.2 Biospecimen Evaluations

Specimens (blood, urine, and nasal swabs) will be used to assess:

- Overall atopic status
- Pre-existing antibodies to polyethylene glycols (Sample analysis will not be completed prior to vaccination; therefore, results will not be used to assess eligibility.)
- Known mediators of systemic reactions due to mast cell activation (e.g., serum tryptase and urinary leukotrienes, prostaglandins, histamine)
- General markers of an acute inflammatory response (e.g., serum IL-6)
- Activation of the classical and alternative complement pathways
- Contact activation of the kinin system
- Activation of basophils and neutrophils
- Unsupervised proteomics, metabolomics, and whole blood transcriptomics
- Analysis of peripheral blood mononuclear cells (PBMCs) may also be explored to assess for new mechanisms
- Evidence of clonal mast cell disease and genetic variants that may increase the risk and/or severity of allergic reactions (e.g. hereditary alpha tryptasemia, clonal mast cell disease)
- Autoantibodies pre and post COVID-19 vaccination

Specific laboratory studies may include those listed below. Assays may be removed or added based on the number and character of reactions seen within the trial. In addition, the timepoints for the conduct of specific laboratory studies may change from what is specified below.

Specimens will be processed at the Laboratory of Allergic Diseases (LAD), Laboratory of Viral Diseases (LVD), Laboratory of Immune System Biology (LISB), and the Laboratory of Bacteriology at the Rocky Mountain Laboratories at NIAID, the Department of Laboratory Medicine (DLM) at NIH (including send-outs to Mayo Clinic), and the Systemic Autoimmunity Branch at the National Institute of Arthritis and Musculoskeletal and Skin Diseases. Coded specimens will also be sent to collaborators at Yale University, Virginia Commonwealth University, Stanford University, University of North Carolina, University of Pittsburgh, KalVista Pharmaceuticals, Inc., and the US FDA for processing.

Blood/serum/plasma:

The following tests may be performed for all participants:

- Whole blood for genetic analysis of the tryptase locus, c-kit locus, and other genetic variants that might influence the risk and/or severity of allergic reactions (Visit 1, pre-dosing)
- Total IgE (Visit 1, pre-dosing Day 1 only)
- Allergen-specific IgE (Visit 1, pre-dosing)
- Anti-Polyethylene glycol (PEG) IgE, IgG, and IgM antibody measurements (Visit 1, pre-dosing, and Visits 3, 4, and 6)
- Anti-SARS-CoV-2 antibodies and functional antibodies (Visit 1, pre-dosing, and Visits 3, 4, and 6)
- Serum total and mature tryptase (Visit 1, pre-dosing, and post-dosing (placebo and vaccine) at 35 minutes and 2 hours)
- Complement activation testing (Visit 1, pre-dosing, and post-dosing (placebo and vaccine) at 35 minutes and 2 hours)
- Flow cytometry for immunophenotyping and assessment of immune activation (Visit 1, pre-dosing, and post-dosing (placebo and vaccine) at 35 minutes, 2 hours, 6 hours, and 24 hours; and Visits 3, 4, and 6)
- Flow cytometry and other assays to assess basophil and neutrophil activation (Visit 1, pre-dosing, and post-dosing (placebo and vaccine) at 35 minutes and 2 hours)
- CBC with differential (Visit 1, pre-dosing, and post-dosing (placebo and vaccine) at 35 minutes, 2 hours, 6 hours, and 24 hours; and Visits 3, 4, and 6)
- Whole blood and single cell transcriptomics and/or CITE-seq (Visit 1, pre-dosing, and post-dosing (placebo and vaccine) at 35 minutes, 2 hours, 6 hours, and 24 hours; and Visits 3, 4, and 6)
- Plasma proteomics and metabolomics (Visit 1, pre-dosing, and post-dosing (placebo and vaccine) at 35 minutes, 2 hours, 6 hours, and 24 hours; and Visits 3, 4, and 6)
- PBMC separation and storage (Visit 1, pre-dosing, and post-dosing (placebo and vaccine) at 35 minutes, 2 hours, 6 hours, and 24 hours; and Visits 3, 4, and 6)
- Plasma Kallikrein (Visit 1, pre-dosing, and post-dosing (placebo and vaccine) at 35 minutes and 2 hours)
- Measurement of platelet activating factor (PAF) and platelet activating factor acetylhydrolase (PAF-AH) as well as neutrophil nets (Visit 1, pre-dosing, and post-dosing (placebo and vaccine) at 35 minutes and 2 hours)
- Serum cortisol level (Visit 1, pre-dosing, and post-dosing (placebo and vaccine) at 35 minutes and 2 hours)
- Metanephrine/normetanephrine (Visit 1, pre-dosing, and post-dosing (placebo and vaccine) at 35 minutes and 2 hours)
- Autoantibody levels (Visit 1, pre-dosing; Visit 3, Visit 4, pre-dosing; and Visit 6)
- Serum pregnancy test for participants of childbearing potential (Visit 1 prior to study intervention)

For subjects who opt in to receiving the booster dose of vaccine at Visit 4, the following tests may be performed pre-dose, 35 minutes (+/-15 minutes) post-dose, and 2 hours (+/-30 minutes) post-dose. Assays may be removed or added based on the number and character of reactions seen within the trial. (Tests indicated for Visit 4 in the previous list will serve as the pre-dose assessment.)

- Serum total and mature tryptase
- CBC with differential
- Complement activation testing
- Plasma Kallikrein
- Measurement of platelet activating factor (PAF) and platelet activating factor acetylhydrolase (PAF-AH) as well as neutrophil nets
- PBMC separation and storage
- Flow cytometry for immunophenotyping and assessment of immune activation
- Flow cytometry and other assays to assess basophil and neutrophil activation
- Whole blood and single cell transcriptomics and/or CITE-seq
- Serum cortisol level
- Metanephrine/normetanephrine
- Serum pregnancy test for participants of childbearing potential (prior to booster vaccination)

Urine:

The following may be performed for all participants:

- Urinary LTE4, N-methyl histamine (NMH), Prostaglandin D2, and 2,3-Dinor-11Beta-Prostaglandin F2 Alpha (Visit 1, pre-dosing and first void(s) following vaccine administration and/or onset of reaction; Visit 4 (participants who opt in to booster dose only), pre-dose and first void post-dose prior to discharge, if possible)

Nasal swab:

The following will be performed for all participants:

- SARS-CoV-2 virus testing by RT-PCR using nasal swab (Visit 1 prior to study intervention)

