4. Investigate mental health characteristics of participants who experience an allergic reaction to the COVID-19 vaccine.
5. Assess psychological impact of allergic reactions to the COVID-19 vaccine and examine changes in stress levels over time.
6. Assess anxiety levels in participants and examine changes in anxiety over time.
7. Assess the proportion of participants who experience no reaction or only a mild reaction (CoFAR Grade 2 or below) to a booster dose of the Pfizer-BioNTech vaccine after previously demonstrating a systemic allergic reaction (CoFAR Grade 2 or 3 reaction regardless of tryptase OR Grade 1 reaction with elevated tryptase [1.2 X baseline plus 2 ng/mL]) to their first full dose of the Pfizer-BioNTech or Moderna COVID-19 vaccine and no allergic reaction or a mild reaction (CoFAR Grade 2 or below) to a subsequent (second) dose of the Pfizer-BioNTech vaccine.
8. Assess the development of autoantibodies after COVID-19 vaccination.

Endpoints:

Primary Endpoint:

1. The proportion of participants who previously demonstrated a systemic allergic reaction (CoFAR Grade 2 or 3 reaction regardless of tryptase OR Grade 1 reaction with elevated tryptase [1.2 X baseline plus 2ng/mL]) to their first full dose of the Pfizer-BioNTech or Moderna COVID-19 vaccine who experience a **systemic allergic reaction** (CoFAR Grade 2 and above reaction regardless of tryptase, or CoFAR grade 1 with elevated tryptase [1.2 X baseline plus 2ng/mL]) within the 3-hour post-vaccine observation period to a subsequent dose of the Pfizer-BioNTech vaccine.

Secondary Endpoints:

2. The proportion of participants who previously demonstrated a systemic allergic reaction (CoFAR Grade 2 or 3 reaction regardless of tryptase OR Grade 1 reaction with elevated tryptase [1.2 X baseline plus 2ng/mL]) to their first full dose of the Pfizer-BioNTech or Moderna COVID-19 vaccine who experience a **severe systemic allergic reaction** (CoFAR grade 3 reaction and above) within the 3-hour post-vaccine observation period to a subsequent dose of the Pfizer-BioNTech vaccine.

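### The primary endpoint needs tryptase to count a Grade 1 reaction over 3 hours, but no tryptase is scheduled after the 2-hour draw, so a late Grade 1 reaction risks being scored a non-event.

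*Combined protocol and SAP*

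**What the plan says.** The primary endpoint in section 1.1 is scored "within the 3-hour post-vaccine observation period to a subsequent dose of the Pfizer-BioNTech vaccine". The qualifying reaction is "CoFAR Grade 2 and above reaction regardless of tryptase, or CoFAR grade 1 with elevated tryptase [1.2 X baseline plus 2ng/mL" (the bracket closes there). Grade 2 and above needs no laboratory value; Grade 1 does.

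Section 8.2.1 schedules Visit 1 blood before each injection and at "approximately 35 minutes (+/-15 minutes), 2 hours (+/-30 minutes), 6 hours (+/-30 minutes), and 24 hours (+/-1 hour) after each study vaccination". Section 8.2.2 assigns assays to these draws. Tryptase is listed as "Serum total and mature tryptase (Visit 1, pre-dosing, and post-dosing (placebo and vaccine) at 35 minutes and 2 hours". Other assays in the same list, such as the blood count, immunophenotyping and proteomics, are also given the 6-hour and 24-hour draws; tryptase is given neither as a post-dose timepoint.

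The list is introduced with "The following tests may be performed for all participants". The same section adds that "Assays may be removed or added based on the number and character of reactions seen within the trial" and that "the timepoints for the conduct of specific laboratory studies may change from what is specified below".

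For reactions that come after the scheduled samples, section 1.3 (footnote t) and sections 4.1 and 8.2.1 provide for extra urine. Reaction-triggered blood for biomarkers is described only for unscheduled visits (section 1.3, footnote b), at the investigator's discretion.

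**The concern.** The measurement that decides whether a Grade 1 reaction counts does not reach the end of the window over which it is to be counted. If a Grade 1 reaction begins after the 2-hour draw, the schedule supplies no tryptase taken after onset and inside the window.

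The plan does not say how such a reaction is classified. Section 1.1 sets no time for the tryptase sample relative to onset. The missing-data rule in section 9.4.2 covers only participants randomized to placebo first who never receive active vaccine. Section 9 says that no formal SAP will be written, so no later document is promised to settle it. The natural default is to treat an unproven elevation as no elevation.

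That error would run one way, toward a lower reaction rate. For a safety endpoint that section 3 says should help guide policy, this is the unfavourable direction.

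**Working it through.** **1. The plan's own figure.** Section 9.2 gives an exact 95% interval of .025 to .556 for 2 reactions in 10. The Clopper-Pearson limits are the 0.025 quantile of Beta(x, n−x+1) and the 0.975 quantile of Beta(x+1, n−x). With x = 2 and n = 10 they are 0.0252 and 0.5561. All 48 intervals in Table 5 reproduce to three decimals, so the precision figures are not in question.

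**2. Uncovered part of the window.** Inputs: a 180-minute window (section 1.1) and a last tryptase draw at 120 ± 30 minutes (section 8.2.1). Uncovered share = (180 − t)/180.

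| Draw at t (min) | Uncovered (min) | Share |
|---|---|---|
| 90 | 90 | 50% |
| 120 (nominal) | 60 | 33% |
| 150 | 30 | 17% |

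**3. Expected loss of events.** Lost events = E × g × L, where E is the number of true primary events, g is the share of them that are tryptase-positive Grade 1, and L is the share of those starting after the draw. The documents give neither g nor L, so both are assumptions. I take E = 20 in 100 (a Table 5 scenario) and g from 10% to 50%.

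- *Late share from the background data.* Section 2.2 reports that 89% of anaphylaxis cases began within 30 minutes, which leaves 11% later. Assuming that this carries over to Grade 1, L = 0.11. Loss: 20 × 0.10 × 0.11 = 0.22 to 20 × 0.50 × 0.11 = 1.1 events. The expected rate falls from 0.200 to between 0.198 and 0.189.
- *Uniform onset over 3 hours (pessimistic).* L = 1/6 to 1/2. Loss: 20 × 0.10 × 1/6 = 0.33 to 20 × 0.50 × 1/2 = 5 events. The expected rate falls to between 0.197 and 0.150.

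**4. Effect on the reported interval.**

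| Observed | Proportion | Exact 95% CI |
|---|---|---|
| 20/100 | 0.20 | 0.127–0.292 |
| 19/100 (one lost) | 0.19 | 0.118–0.281 |
| 15/100 (five lost) | 0.15 | 0.086–0.235 |

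The protocol expects that enrolment may fall short of 100. At N = 20 a single lost event moves the estimate by 1/20 = 5 points, for example from 3/20 (0.15; 0.032–0.379) to 2/20 (0.10; 0.012–0.317). That shows the size of one step, not the expected loss. With three true events and L = 0.11, the expected loss is 3 × (0.10 to 0.50) × 0.11 = 0.03 to 0.17 events.

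**The case against.** A reader might infer that a late Grade 1 reaction can never qualify, or that events are in fact being under-counted. The documents support neither.

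- **Discretion exists.** Section 8.2.2 lets assays be added and timepoints moved. Section 8.3 allows further procedures, including laboratory evaluations, to characterize an adverse event. Blood is drawn at 6 hours for testing and storage, and section 4.1 refers treatment of reactions to a manual of procedures that is not among the documents. This stands, and it is why the point is a risk rather than a certainty. It does not close the gap: discretion exercised after a reaction is seen is not a rule, and it makes ascertainment depend on who acts.
- **Not a non-event by definition.** The endpoint does not require a post-onset sample, so the scoring of these cases is unspecified, not fixed. This stands too, and is itself something to repair.
- **The effect is small.** The 11% includes onsets between 30 minutes and the 2-hour draw, which the schedule covers. Equally, it describes reported anaphylaxis rather than Grade 1 reactions, so it is not a proven ceiling.
- **Other reporting catches these reactions.** A secondary endpoint counts Grade 1 or 2 reactions whatever the tryptase, and the schedule is the same after placebo and vaccine. Both are true. But the primary endpoint is a single proportion on active vaccine, and neither feature corrects it.
- **The permissive wording is generic.** The same list contains the serum pregnancy test, which section 8.2.1 makes compulsory. A reader might infer that the plan intends tryptase to be optional or removable; that reads too much into a list heading. It is a matter for clarification only.
- **Too late for new draws.** Section 4.1 notes that as of September 15, 2022 only two participants had still to complete the 5-month visit, which suggests that Visit 1 dosing is largely or wholly done. This limits the remedy but does not remove it.

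**Conclusion.** The point holds as a gap in coverage. The endpoint window is 3 hours, and its last 17% to 50% (33% nominal) has no scheduled post-onset tryptase, although Grade 1 reactions need one to count. Any resulting error lowers the primary reaction rate and is confined to Grade 1.

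The size is probably small: about 0.2 to 1.1 events per 20 true events if the anaphylaxis onset figure carries over, and 0.3 to 5 if onset were uniform. Both ranges rest on an assumed Grade 1 share of 10% to 50%. This is a cheap improvement to an endpoint's measurement. It is not evidence that the reported rate will be materially wrong.

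**What to change.** 1. In section 8.2.2, add tryptase on the 6-hour sample already drawn, at least for any Grade 1 reaction starting after the 2-hour draw and within 3 hours, on either injection day. For participants already dosed, this means assaying stored 6-hour material if a suitable aliquot was kept.
2. Where dosing is still going on, take one post-onset tryptase tube from the line already in place for such a reaction.
3. State how a Grade 1 reaction without a timely post-onset tryptase is classified in the main analysis, and report a sensitivity analysis of the primary proportion that counts these reactions as events. This is needed even with item 1, because the documents do not show whether an elevation would still be present at 6 hours.
4. As a wording clarification, state that tryptase at the endpoint timepoints is required and is not subject to the provision for removing assays.

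The cost is a few extra tryptase assays, one additional line in the results table, and a short amendment to section 8.2.2 and to the analysis text in section 9.4.2. No extra visit is needed.
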